### **Hamilton Anxiety Scale**

The Hamilton Anxiety Rating Scale (HAM-A) measures psychic anxiety and somatic anxiety symptoms based on a clinical assessment and patient interview. The scale has 14 items, with each item rated from 0-4, ranging from not present to very severe. A maximum score of 56 indicates the most severe case. ([Hamilton 1959](#)).

The HAM-A will be administered at baseline, V106 and V201.

## **Koukopoulos Mixed Depression Rating Scale**

The Koukopoulos Mixed Depression Rating Scale (KMDRS) assesses the excitatory or mixed nature in patients suffering from a Major Depressive Episode (MDE) as defined by DSM-5 criteria. This scale is meant to be used in conjunction with another scale that assess typical depression and anxiety symptoms. The scale contains 14 items to be evaluated by clinical assessment and patient interview on symptoms potentially experienced over the past week. Overall score increases with severity of symptoms and has a maximum score of 51. ([Sani et al 2018](#)).

The KMDRS will be administered at all visits except screening.

### **8.5.2 Pharmacokinetics**

Pharmacokinetic (PK) samples will be collected at the time points defined in the Assessment schedule ([Table 8-1](#)). Follow instructions outlined in the SOM and in the Bioanalytical study specification regarding sample collection, numbering, processing and shipment.

In order to better define the PK profile, the timing of the PK sample collection may be altered based on emergent data. The number of samples/blood draws and total blood volume collected will not exceed those stated in the protocol.

PK samples should be collected in all patients to avoid unblinding. Only the samples from patients treated with MIJ821 will be analyzed

#### **Pharmacokinetic analytical method(s)**

Commercially Confidential Information

#### **Pharmacokinetic parameters**

Commercially Confidential Information

Commercially Confidential Information

## **9 Study discontinuation and completion**

### **9.1 Discontinuation**

#### **9.1.1 Discontinuation of study treatment**

Discontinuation of study treatment for a subject occurs when study treatment is stopped earlier than the protocol planned duration, and can be initiated by either the subject or the investigator.

The investigator must discontinue study treatment for a given subject if, he/she believes that continuation would negatively impact the subject's well-being.

Study treatment must be discontinued under the following circumstances:

- Subject's decision
- Pregnancy
- Any situation in which study participation might result in a safety risk to the subject
- CTC-AE Grade 3 or higher adverse event unless it can be conclusively shown that AE is not related to study treatment.
- Severe hypersensitivity reaction such as anaphylaxis
- Any protocol deviation that results in a significant risk to subject safety
- Adverse events, abnormal laboratory values or abnormal test result that indicate a safety risk to the subject

If discontinuation of study treatment occurs, the investigator should make a reasonable effort to understand the primary reason for the subject's premature discontinuation of study treatment and record this information.

Subjects who discontinue study treatment or who decide they do not wish to participate in the study further should NOT be considered withdrawn from the study UNLESS they withdraw their consent (see [Section 9.1.2](#)). Where possible, subjects should return for V299 and complete the assessments indicated in the [Assessment schedule](#) for this visit. If subjects fail to return for these assessments for unknown reasons, every effort (e.g. telephone, e-mail, letter) should be made to contact the subject/pre-designated contact as specified in [Section 9.1.3](#). This contact should preferably be done according to the study visit schedule.

If the subject cannot or is unwilling to attend any visit(s), the site staff should maintain regular telephone contact with the subject, or with a person pre-designated by the subject. This telephone contact should preferably be done according to the study visit schedule.

After study treatment discontinuation, at a minimum, in abbreviated visits, the following data should be collected at clinic visits or via telephone/email contact:

- new / concomitant treatments
- adverse events/Serious Adverse Events

The investigator must also contact the IRT to register the subject's discontinuation from study treatment.

If discontinuation occurs because treatment code has been broken, please refer to Emergency breaking of treatment code section.

### **9.1.1.1 Replacement policy**

Subjects who are withdrawn from the study for reasons other than safety, the decision to replace them by an equal number of newly enrolled subjects will be taken by the Sponsor.

### **9.1.2 Withdrawal of informed consent**

Subjects may voluntarily withdraw consent to participate in the study for any reason at any time. Withdrawal of consent occurs only when a subject:

- Does not want to participate in the study anymore

and

- Does not allow further collection of personal data

In this situation, the investigator should make a reasonable effort (e.g. telephone, e-mail, letter) to understand the primary reason for the subject's decision to withdraw his/her consent and record this information.

Study treatment must be discontinued and no further assessments conducted, and the data that would have been collected at subsequent visits will be considered missing.

Further attempts to contact the subject are not allowed unless safety findings require communicating or follow-up.

All efforts should be made to complete the assessments prior to study withdrawal. A final evaluation at the time of the subject's study withdrawal should be made as detailed in the [assessment table](#).

Novartis will continue to keep and use collected study information (including any data resulting from the analysis of a subject's samples until the time of withdrawal) according to applicable law.

For US: All biological samples not yet analyzed at the time of withdrawal may still be used for further testing/analysis in accordance with the terms of this protocol and of the informed consent form.

For EU: All biological samples not yet analyzed at the time of withdrawal will no longer be used, unless permitted by applicable law. They will be stored according to applicable legal requirements.

### **9.1.3 Lost to follow-up**

For subjects whose status is unclear because they fail to appear for study visits without stating an intention to discontinue or withdraw, the investigator must show "due diligence" by documenting in the source documents steps taken to contact the subject, e.g. dates of telephone calls, registered letters, etc. A subject should not be considered as lost to follow-up until due diligence has been completed or until the end of the study.

#### **9.1.4 Study stopping rules**

The study will be stopped, and no further enrollment will take place pending a full safety review, if any of the following criteria are met:

- At least 5 subjects in any single treatment arm experience an AE of Grade 3 or higher according to the CTC-AE V5.0 and is potentially related to study treatment
- Two or more treatment-emergent SAEs, except those that are clearly and incontrovertibly due to extraneous causes;
- The Sponsor considers that the number and/or severity of AEs justify putting the study on hold.

The study may resume following the safety review, if the Investigator and Sponsor agree it is safe to proceed.

#### **9.1.5 Early study termination by the sponsor**

The study can be terminated by Novartis at any time.

Reasons for early termination:

- Unexpected, significant, or unacceptable safety risk to subjects enrolled in the study
- Decision based on recommendations from applicable board(s) after review of safety and efficacy data
- Discontinuation of study drug development

In taking the decision to terminate, Novartis will always consider subject welfare and safety. Should early termination be necessary, subjects must be seen as soon as possible and treated as a prematurely withdrawn subject. The investigator may be informed of additional procedures to be followed in order to ensure that adequate consideration is given to the protection of the subject's interests. The investigator or sponsor depending on local regulation will be responsible for informing IRBs/IECs of the early termination of the trial.

## **9.2 Study completion and post-study treatment**

Study completion is defined as when the last subject finishes their study completion visit, and any repeat assessments associated with this visit have been documented and followed-up appropriately by the Investigator, or in the event of an early study termination decision, the date of that decision (e.g. each subject will be required to complete the study in its entirety and thereafter no further study treatment will be made available to them).

All randomized and/or treated subjects should have a safety follow-up call conducted 30 days after last administration of study treatment. The information collected is kept as source documentation. All SAEs reported during this time period must be reported as described in [Section 10.1.3](#) and SOM. Documentation of attempts to contact the subject should be recorded in the source documentation.

## 10 Safety monitoring and reporting

### 10.1 Definition of adverse events and reporting requirements

#### 10.1.1 Adverse events

An adverse event (AE) is any untoward medical occurrence (e.g., any unfavorable and unintended sign [including abnormal laboratory findings], symptom or disease) in a subject or clinical investigation subject after providing written informed consent for participation in the study. Therefore, an AE may or may not be temporally or causally associated with the use of a medicinal (investigational) product.

The investigator has the responsibility for managing the safety of individual subject and identifying adverse events.

Novartis qualified medical personnel will be readily available to advise on trial related medical questions or problems.

The occurrence of adverse events must be sought by non-directive questioning of the subject at each visit during the study. Adverse events also may be detected when they are volunteered by the subject during or between visits or through physical examination findings, laboratory test findings, or other assessments.

Adverse events must be recorded in the Adverse Events CRF under the signs, symptoms or diagnosis associated with them, accompanied by the following information (as far as possible) (if the event is serious refer to [Section 10.1.2](#)):

1. The Common Toxicity Criteria (CTC) AE grade (version 5.0 or higher). A copy of the CTCAE grading will be provided separately in the SOM.

Adverse events will be assessed and graded according to the Common Terminology Criteria for Adverse Events (CTCAE) version 5.0

2. its relationship to the study treatment and other investigational treatment. If the event is due to lack of efficacy or progression of underlying illness (i.e. progression of the study indication) the assessment of causality will usually be 'Not suspected'. The rationale for this guidance is that the symptoms of a lack of efficacy or progression of underlying illness are not caused by the trial drug, they happen in spite of its administration and/or both lack of efficacy and progression of underlying disease can only be evaluated meaningfully by an analysis of cohorts, not on a single subject
3. its duration (start and end dates) or if the event is ongoing, an outcome of not recovered/not resolved must be reported.
4. whether it constitutes a SAE (see [Section 10.1.2](#) for definition of SAE) and which seriousness criteria have been met
5. action taken regarding with study treatment.

All adverse events must be treated appropriately. Treatment may include one or more of the following:

- Dose not changed
- Dose Reduced/increased
- Drug interrupted/withdrawn

6. its outcome.

Conditions that were already present at the time of informed consent should be recorded in medical history of the subject.

Adverse events (including lab abnormalities that constitute AEs) should be described using a diagnosis whenever possible, rather than individual underlying signs and symptoms.

Adverse event monitoring should be continued for at least 30 days following the last dose of study treatment.

Once an adverse event is detected, it must be followed until its resolution or until it is judged to be permanent (e.g. Continuing at the end of the study), and assessment must be made at each visit (or more frequently, if necessary) of any changes in severity, the suspected relationship to the interventions required to treat it, and the outcome.

Information about adverse drug reactions for the investigational drug can be found in the Investigator Brochure (IB).

Abnormal laboratory values or test results constitute adverse events only if they fulfill at least one of the following criteria:

- they induce clinical signs or symptoms
- they are considered clinically significant
- they require therapy

Clinically significant abnormal laboratory values or test results must be identified through a review of values outside of normal ranges/clinically notable ranges, significant changes from baseline or the previous visit, or values which are considered to be non-typical in subjects with the underlying disease.

Follow the instructions found in the SOM for data capture methodology regarding AE collection for subjects that fail screening.

### **10.1.2 Serious adverse events**

An SAE is defined as any adverse event [appearance of (or worsening of any pre-existing)] undesirable sign(s), symptom(s) or medical conditions(s)) which meets any one of the following criteria:

- fatal
- life-threatening

Life-threatening in the context of a SAE refers to a reaction in which the subject was at risk of death at the time of the reaction; it does not refer to a reaction that hypothetically might have caused death if it were more severe (please refer to the ICH-E2D Guidelines).

- results in persistent or significant disability/incapacity
- constitutes a congenital anomaly/birth defect
- requires inpatient hospitalization or prolongation of existing hospitalization, unless hospitalization is for:
  - routine treatment or monitoring of the studied indication, not associated with any deterioration in condition.
  - elective or pre-planned treatment for a pre-existing condition that is unrelated to the indication under study and has not worsened since signing the informed consent
  - social reasons and respite care in the absence of any deterioration in the subject's general condition
  - treatment on an emergency outpatient basis for an event not fulfilling any of the definitions of a SAE given above and not resulting in hospital admission
- is medically significant, e.g. defined as an event that jeopardizes the subject or may require medical or surgical intervention to prevent one of the outcomes listed above

Medical and scientific judgment should be exercised in deciding whether other situations should be considered serious reactions, such as important medical events that might not be immediately life threatening or result in death or hospitalization but might jeopardize the subject or might require intervention to prevent one of the other outcomes listed above. Such events should be considered as "medically significant". Examples of such events are intensive treatment in an emergency room or at home for allergic bronchospasm, blood dyscrasias or convulsions that do not result in hospitalization or development of dependency or abuse (please refer to the ICH-E2D Guidelines).

Any suspected transmission via a medicinal product of an infectious agent is also considered a serious adverse reaction.

All reports of intentional misuse and abuse of the product are also considered serious adverse event irrespective if a clinical event has occurred.

### 10.1.3 SAE reporting

To ensure subject safety, every SAE, regardless of causality, occurring after the subject has provided informed consent and until 30 days following the last administration of study treatment must be reported to Novartis safety within 24 hours of learning of its occurrence. Detailed instructions regarding the submission process and requirements are to be found in the investigator folder provided to each site.

**Event common in the subject population under study:** during studies, the unblinding of single SAEs, that are relatively common in the subject population under study, for SUSAR reporting, often does not increase the understanding of safety, and can damage the integrity of the blinded nature and analysis of a study. The study protocol may then contain a "Table of AEs Commonly Seen in the Subject Population" that are still captured by the investigator as AEs and SAEs in the CRF and reported to Novartis for the SAEs, but they would not be unblinded

during the course of the study, even if considered "related" to study treatment by the reporting investigator, nor reported on an expedited basis to regulatory authorities.

**IMPORTANT:** To comply with regulations, all suspected, unexpected, serious adverse reactions (SUSARs) occurring in a clinical trial must be reported in an expedited timeframe (7 or 15 days) to competent authorities.

Consider the following 2 categories to determine SAE reporting timeframes:

1. Screen Failures (e.g. a subject who is screened but is not treated or randomized): SAEs occurring after the subject has provided informed consent until the time the subject is deemed a Screen Failure must be reported to Novartis.
2. Randomized OR Treated Subjects: SAEs collected between time subject signs ICF until 30 days after the subject has discontinued or stopped study treatment.

All follow-up information for the SAE including information on complications, progression of the initial SAE and recurrent episodes must be reported as follow-up to the original episode within 24 hours of the investigator receiving the follow-up information. An SAE occurring at a different time interval or otherwise considered completely unrelated to a previously reported one must be reported separately as a new event.

If the SAE is not previously documented in the Investigator's Brochure or Package Insert (new occurrence) and is thought to be related to the study treatment, a Novartis Chief Medical Office and Patient Safety (CMO & PS) Department associate may urgently require further information from the investigator for health authority reporting. Novartis may need to issue an Investigator Notification (IN) to inform all investigators involved in any study with the same study treatment that this SAE has been reported.

Suspected Unexpected Serious Adverse Reactions (SUSARs) will be collected and reported to the competent authorities and relevant ethics committees in accordance with EU Guidance 2011/C 172/01 or as per national regulatory requirements in participating countries.

Any SAEs experienced after the 30 day period following the last administration of study treatment should only be reported to Novartis Safety if the investigator suspects a causal relationship to study treatment.

#### **10.1.4 Pregnancy reporting**

To ensure subject safety, each pregnancy occurring after signing the informed consent must be reported to Novartis within 24 hours of learning of its occurrence. The pregnancy should be followed up to determine outcome, including spontaneous or voluntary termination, details of the birth, and the presence or absence of any birth defects, congenital abnormalities, or maternal and/or newborn complications. The newborns will be followed up for 3 months after delivery.

Pregnancy should be recorded and reported by the investigator to the Novartis Chief Medical Office and Patient Safety (CMO&PS). Pregnancy follow-up should be recorded on the same form and should include an assessment of the possible relationship to the study treatment any pregnancy outcome. Any SAE experienced during pregnancy must be reported.

Pregnancy outcomes should be collected for the female partners of any males who took study treatment in this study. Consent to report information regarding these pregnancy outcomes should be obtained from the mother.

### 10.1.5 Reporting of study treatment errors including misuse/abuse

Medication errors are unintentional errors in the prescribing, dispensing, administration or monitoring of a medicine while under the control of a healthcare professional, subject or consumer (EMA definition).

Misuse refers to situations where the medicinal product is intentionally and inappropriately used not in accordance with the protocol.

Abuse corresponds to the persistent or sporadic, intentional excessive use of a medicinal product, which is accompanied by harmful physical or psychological effects.

Study treatment errors and uses outside of what is foreseen in the protocol will be collected in the DAR (dose administration record) eCRF irrespective of whether or not associated with an AE/SAE and reported to Safety only if associated with an SAE. Misuse or abuse will be collected and reported in the safety database irrespective of it being associated with an AE/SAE within 24 hours of Investigator's awareness.

**Table 10-1 Guidance for capturing the study treatment errors including misuse/abuse**

Treatment error type	Document in Dose Administration (DAR) eCRF (Yes/No)	Document in AE eCRF	Complete SAE form
Unintentional study treatment error	Yes	Only if associated with an AE	Only if associated with an SAE
Misuse/Abuse	Yes	Yes	Yes, even if not associated with a SAE

For more information on AE and SAE definition and reporting requirements, please see [Section 10.1.1](#) and [Section 10.1.2](#), respectively.

## 10.2 Additional Safety Monitoring

Not applicable.

### 10.2.1 Liver safety monitoring

To ensure subject safety and enhance reliability in determining the hepatotoxic potential of an investigational drug, a standardized process for identification, monitoring and evaluation of liver events has to be followed.

The following two categories of abnormalities / adverse events have to be considered during the course of the study (irrespective of whether classified/reported as AE/SAE):

- Liver laboratory triggers, which will require repeated assessments of the abnormal laboratory parameter
- Liver events, which will require close observation, follow-up monitoring and completion of the standard base liver CRF pages

Please refer to [Table 16-1](#) in Appendix 1 for complete definitions of liver laboratory triggers and liver events.

Every liver event defined in [Table 16-1](#) should be followed up by the investigator or designated personnel at the trial site, as summarized below. Additional details on actions required in case of liver events are outlined in [Table 16-2](#). Repeat liver chemistry tests (ALT, AST, TBL, PT/INR, ALP and G-GT) to confirm elevation.

- These liver chemistry repeats will be performed using the central laboratory. If results will not be available from the central laboratory, then the repeats can also be performed at a local laboratory to monitor the safety of the subject. If a liver event is subsequently reported, any local liver chemistry tests previously conducted that are associated with this event should have results reported on the unplanned local laboratory CRF
- If the initial elevation is confirmed, close observation of the subject will be initiated, including consideration of treatment interruption if deemed appropriate.
- Discontinuation of the investigational drug (refer to [Section 9.1.1](#)), if appropriate
- Hospitalization of the subject if appropriate
- Causality assessment of the liver event
- Thorough follow-up of the liver event should include
  - These investigations can include based on investigator's discretion: serology tests, imaging and pathology assessments, hepatologist's consultancy; obtaining more detailed history of symptoms and prior or concurrent diseases, history of concomitant drug use, exclusion of underlying liver disease

All follow-up information, and the procedures performed must be recorded as appropriate in the CRF.

Refer to the SOM for additional details.

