### **3 Study design**

This is a non-confirmatory, multi-center, 6-treatment arm in the European countries and 5-treatment arm in the USA (no ketamine arm), randomized, subject and investigator blinded, parallel group, placebo controlled study in treatment-resistant depression patients. The study will randomize approximately 66 Subjects and while the study design utilizes an outpatient visit schedule, the study allows for the inclusion of subjects seeking treatment for their disease from both an 'inpatient' or 'outpatient' clinic setting.

A screening period of maximum 4 weeks will be used to assess eligibility. Patients who meet the eligibility criteria at screening will proceed to baseline evaluations on Day-1 or Day 1. All baseline safety evaluation results must be available prior to randomization. At the baseline visit, eligible subjects will be randomized to one of the treatment arms. Randomized subjects will enter a 36- day treatment period, receiving at each treatment visit, a 40-minute infusion with a safety observation period of 2-4 hours (i.e. a minimum of 2 hours) post the start of

infusion. If the subject reports no dissociative symptoms and no suicidal symptoms, the subject will be allowed to leave the clinical treatment setting. Visits to assess efficacy and safety are scheduled at 24 hours, 48 hours (if applicable) and every week during the treatment period. If 48 hour visit (V103) is conducted, then all assessments should be completed. The assessment to address the primary objective will be performed at 24 hour post-dose. Safety assessments will include physical examinations, ECGs, vital signs, standard clinical laboratory evaluations (hematology, blood chemistry, and urinalysis), adverse event and serious adverse event monitoring. At the conclusion of the treatment period (Day 1 - Day 36), subjects will enter a 5-week follow up period consisting of two follow visits approximately 1 week (Day 43) and 3 weeks (Day 57) after the last study drug administration and an end of study completion visit (Day 71) The total duration for each subject in the study is maximum 14-weeks including screening and baseline. No interim analysis is planned. The study design is summarized in [Figure 3-1](#) below for the European countries (same study design without the ketamine arm in the USA).

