#### **4.5.1 Blood sample volume**

A volume smaller than a typical blood donation is planned to be collected over a period of 6 weeks, from each subject as part of the study (representing a total of around 220 ml). Additional samples may be required for safety monitoring.

Timing of blood sample collection is outlined in the [Assessment schedule](#).

A summary blood log is provided in the SOM. Instructions for all sample collection, processing, storage and shipment information are also available in the SOM and central laboratory manual.

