**Table 8-2 Laboratory Assessments**

Test Category	Test Name
Hematology	Hemoglobin, hematocrit, red blood cell count, white blood cell count with differential (e.g., neutrophils, basophils, eosinophils, monocytes, lymphocytes) and platelet count will be measured.
Chemistry	Albumin, alkaline phosphatase, total bilirubin, bicarbonate/carbon dioxide (CO 2 ), calcium, cholesterol, chloride, creatinine, creatinine kinase (CK), GGT, glucose, lactic dehydrogenase (LDH), inorganic phosphorus, lipase, amylase, magnesium, potassium, total protein, AST, ALT, sodium, triglycerides, blood urea nitrogen (BUN) uric acid. If the total bilirubin concentration is increased above 1.5 times the upper limit of normal, direct and indirect reacting bilirubin should be differentiated. Thyroid Stimulating Hormone (TSH) level will be analyzed as well. In case of abnormal TSH value, additional evaluation will be performed (triiodothyronine [T3] and thyroxine [T4]).
Urinalysis	A midstream urine sample (approximately 30 mL) will be obtained from subjects with no urinary catheters, in order to avoid contamination with epithelial cells and sediments, and allow proper assessments. A semi-quantitative "dipstick" evaluation for the following parameters will be performed: specific gravity, pH, glucose, protein, bilirubin, ketones, nitrite, leukocytes and blood. If the dipstick result is positive for protein, nitrite, leucocytes and/or blood, the sample will be sent for microscopic analysis of WBC, RBC and casts.

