**Table 16-2 Follow Up Requirements for Liver Events and Laboratory Triggers**

Criteria	Actions required	Follow-up monitoring
Potential Hy's Law case a	
 
Discontinue the study treatment immediately
 
Hospitalize, if clinically appropriate
 
Establish causality
 
Complete liver CRF
 
	ALT, AST, TBL, Alb, PT/INR, ALP and $\gamma$ GT until resolution c (frequency at investigator discretion)
ALT or AST		
> 5 × ULN	
 
Discontinue the study treatment immediately
 
Hospitalize if clinically appropriate
 
Establish causality
 
Complete liver CRF
 
	ALT, AST, TBL, Alb, PT/INR, ALP and $\gamma$ GT until resolution c (frequency at investigator discretion)
> 3 × ULN and INR > 1.5	
 
Discontinue the study treatment immediately
 
Hospitalize, if clinically appropriate
 
Establish causality
 
Complete liver CRF
 
	ALT, AST, TBL, Alb, PT/INR, ALP and $\gamma$ GT until resolution c (frequency at investigator discretion)
> 3 × ULN accompanied by symptoms b	
 
Discontinue the study treatment immediately
 
Hospitalize if clinically appropriate
 
Establish causality
 
Complete liver CRF
 
	ALT, AST, TBL, Alb, PT/INR, ALP and $\gamma$ GT until resolution c (frequency at investigator discretion)
> 3 to ≤ 5 × ULN (subject is asymptomatic)	
 
Repeat LFT within the next week
 
If elevation is confirmed, initiate close observation of the subject
 
	Investigator discretion Monitor LFT within 1 to 4 weeks
ALP (isolated)		
> 2 × ULN (in the absence of known bone pathology)	
 
Repeat LFT within 48 hours
 
If elevation persists, establish causality
 
Complete liver CRF
 
	Investigator discretion Monitor LFT within 1 to 4 weeks or at next visit

Criteria	Actions required	Follow-up monitoring
TBL (isolated)		

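### The INR-based liver stop rule needs a test the plan does not schedule, and the one-week repeat window lets one more infusion be given before the INR is known

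*Protocol*

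**What the plan says.** Protocol Table 16-2 (Appendix 1) has a row for ALT or AST "> 3 × ULN and INR > 1.5", with the action "Discontinue the study treatment immediately". Four other rows carry the same unconditional action.

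The planned laboratory work contains no coagulation test. Section 3 describes it as "standard clinical laboratory evaluations (hematology, blood chemistry, and urinalysis"). Table 8-2 has the same three categories, and its chemistry list ends with "lipase, amylase, magnesium, potassium, total protein, AST, ALT, sodium, triglycerides, blood urea nitrogen (BUN) uric acid", plus TSH.

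For ALT or AST above 3 and up to 5 × ULN without symptoms, Table 16-2 says "Repeat LFT within the next week", followed by closer monitoring if the rise is confirmed. Section 10.2.1 distinguishes liver events from "Liver laboratory triggers, which will require repeated assessments of the abnormal laboratory parameter". Further down, after a sentence about liver events, it adds: "Repeat liver chemistry tests (ALT, AST, TBL, PT/INR, ALP and G-GT) to confirm elevation".

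Section 6.5 rules out dose adjustments and interruptions in infusions, and refers a missed weekly dose to the medical monitor. Table 8-1 places infusion visits on Days 1, 8, 15, 22, 29 and 36.

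**The concern.** A rule that says to stop at once should be decidable when the abnormal result arrives, or very soon after. This one is not. The plan gives the site the ALT and AST but not the INR that separates an immediate stop from watchful repetition. Without the INR, the subject falls by default into the milder row, and that row's time limit is as long as the dosing interval.

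What is at stake is the safety of a small subgroup: asymptomatic subjects with a moderate transaminase rise who also have impaired clotting. They could be infused again although the protocol intends them to be off treatment.

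**Working it through.** The protocol states no figure to reproduce. The check sets each stop rule against the planned tests and then compares the repeat window with the dosing days.

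**1. Which immediate-stop rows can be recognised from what is planned?**

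| Unconditional stop row (Table 16-2) | What it needs | Available as planned? |
|---|---|---|
| Potential Hy's Law | ALT/AST, TBL, ALP | Yes, Table 8-2 |
| ALT/AST > 5 × ULN | ALT/AST | Yes, Table 8-2 |
| ALT/AST > 3 × ULN with INR > 1.5 | ALT/AST and INR | ALT/AST yes, INR no |
| ALT/AST > 3 × ULN with symptoms | ALT/AST, symptoms | Yes |
| Jaundice | Clinical sign | Yes |

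Rows that need an unplanned test: 1 of 5. Table 8-2 lists 24 chemistry analytes plus TSH, 25 in all, and none is PT or INR. Isolated TBL above 2 × ULN is not counted, because that stop depends on persistence at repeat.

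**2. Where does the subject land?** With ALT or AST above 3 and up to 5 × ULN, no symptoms, no Hy's Law bilirubin, no jaundice and INR unknown, the only row that fits is the asymptomatic trigger row. Table 16-2 has 10 rows and names PT/INR as follow-up in 6 of them. All 6 are rows where drug is stopped (for isolated TBL above 2 × ULN, if it persists). The trigger row, where the INR would decide the action, is not among them.

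**3. Does the repeat bring an INR?**
- In favour: the 10.2.1 panel names PT/INR and exists to confirm an elevation. The same section foresees a liver event being reported after repeat tests have been done. Its next step, closer observation once the rise is confirmed, matches the trigger rows rather than the immediate-stop rows.
- Against: the panel follows a sentence about liver events, the trigger bullet asks only for the abnormal parameter, and LFT is not defined.

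The first reading is the better one. The second is not excluded.

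**4. How many infusions can come first?** The gaps are 8 − 1, 15 − 8, 22 − 15, 29 − 22 and 36 − 29, each 7 days. Assume the sample is drawn on infusion day *d* (the laboratory visit days are not visible) and the turnaround is *r* days (not given in the documents).
- ALT/AST known: *d* + *r*
- Latest permitted repeat: *d* + *r* + 7
- INR known at the latest: *d* + 2*r* + 7

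The infusion on *d* + 7 can fall before the INR is known. The infusion on *d* + 14 could do so only if 2*r* + 7 > 14, that is *r* > 3.5 days. With a turnaround no longer than that, the count is 0 (prompt repeat, or trigger found at or after Day 36) to 1.

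**The case against.** The strongest reply is that the plan already contains the test and enough discretion. Read as a whole, 10.2.1 brings PT/INR with the confirmatory repeat. A week is a maximum. A local laboratory may be used when central results will not be available. Treatment interruption may be considered after confirmation. Section 9.1.1 requires discontinuation for abnormal results that indicate a safety risk. Section 4.5.1 states: "Additional samples may be required for safety monitoring". Section 14 allows extra safety assessments case by case. Both 10.2.1 and 8.4.1 point to documents not seen here, where a reflex INR could be specified.

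Much of this stands. A reader might infer that the INR is never required and the stop rule is a dead letter. The documents do not support that, for the reasons in step 3 of the working. Nor do they support counting every remaining infusion as at risk: symptoms, a rise above 5 × ULN, Hy's Law bilirubin, jaundice or investigator action would each end dosing, and after Day 36 no infusion remains.

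The timing is not answered. The safeguards are discretionary or come only after the elevation is confirmed, whereas the stop is mandatory and immediate. Section 6.5 also conflicts with the interruption that 10.2.1 contemplates.

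**Conclusion.** The point holds as a timing gap with a secondary ambiguity. One of five immediate-stop rows cannot be decided from planned tests when the elevation is found, and a subject who already meets it can receive 0 to 1 further infusion within the plan as written. That infusion need not be active drug: there are placebo and ketamine arms, and the Protocol summary refers to bi-weekly as well as weekly MIJ821 (arm details are redacted).

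This assumes that the repeat includes PT/INR, that laboratory turnaround is short relative to the dosing interval, and that no reflex INR is set out in the SOM or laboratory manual. How many of the approximately 66 subjects would be affected cannot be estimated, because the documents give no liver-event rate.

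A reader might conclude that every subject needs a baseline INR. The rule uses an absolute threshold of 1.5, so it can be applied without one. The primary endpoint, 24 hours after the first dose, is unaffected, as are the analyses.

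**What to change.** 1. **Table 16-2, ALT/AST > 3 to ≤ 5 × ULN row.** Replace "Repeat LFT within the next week" with: *Repeat ALT, AST, TBL, ALP, G-GT and PT/INR within 48 hours, and in any case before the next infusion; do not infuse until the INR is known.* Allow a local laboratory, as 10.2.1 does. The table already uses 48 hours for isolated ALP and TBL above 2 × ULN.
2. **Table 8-2.** List PT/INR as a reflex test for any ALT or AST above 3 × ULN. The table already has conditional tests, for raised bilirubin and abnormal TSH.
3. **Section 10.2.1, trigger bullet.** For ALT/AST triggers, refer to the same panel instead of the abnormal parameter alone.
4. **Section 6.5.** Exempt this safety hold from the ban on interruptions, and handle it as a missed dose with medical monitor contact.

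If the SOM or laboratory manual already requires a reflex INR, item 2 can be a cross-reference; the hold and the change to 6.5 should still be confirmed.

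The cost is one coagulation sample in the few subjects with ALT or AST above 3 × ULN, central laboratory set-up for PT/INR, and a possible delayed or missed weekly dose. No threshold or analysis changes.
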